## 6.1.3 Imatinib side effects

The most common side effects of imatinib include nausea, diarrhea, headaches, leg cramps, fluid retention, visual disturbances, rash, weight gain, and reduced number of blood cells (any cell line can be affected). Imatinib is an immune suppressant and increases risks of common and uncommon infections.

Severe systolic congestive heart failure is an uncommon but recognized side effect of imatinib and mice treated with large doses of imatinib show toxic damage to myocardiocytes. Hypoxemia has been noted in one individual with LAM.

Since imatinib is mainly metabolised via the liver enzyme CYP3A4, substances such as ketoconazole, itraconazole, clarithromycin, and grapefruit juice can increase the plasma concentration of the drug. Conversely, CYP3A4 inducers like rifampin and St. John's Wort reduce the drug's activity. These medications will be prohibited during the study. A known interaction between imatinib and sirolimus in which sirolimus levels rise will be monitored during the study.

Imatinib also acts as an inhibitor of CYP3A4, 2C9 and 2D6, increasing the plasma concentrations of simvastatin, cyclosporin, pimozide, warfarin, and metoprolol. Imatinib also reduces plasma levels of levothyroxin via an unknown mechanism. INR, Cholesterol, T4, and TSH will be measured during the study for all individuals.

An imatinib dose reduction to 200 mg daily will be permitted should a participant experience persistent side effects.

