## 6.3 Adverse Events

An adverse event (AE) is any untoward medical occurrence in a study subject. This may include symptom(s), illness, clinically significant abnormal laboratory value or change in value, or worsening in a subject during a clinical study. Since one of the specific aims of the study is to establish the safety of imatinib in LAM affected individuals, it is the goal of the investigators to capture every AE.

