## 6.3.1 Procedures for Adverse Events

Event, date of onset, severity, duration, and relationship to sirolimus or imatinb (if it can be determined) will be recorded on the study AE forms. All adverse events will be followed until they are adequately resolved or stabilized, or for 1 month following study completion, whichever comes first.

If an adverse event occurs during a study visit the study coordinator should first insure the participant receives any needed medical attention. If the study coordinator is notified by phone, the coordinator should confirm that the participant has received medical attention. The study coordinator should then notify the site Principal Investigator and complete the Adverse Event Form within seven days of learning of the event. Study coordinators will comply with local regulations and policies when notifying the institutional IRB.

The following general definitions for rating severity should be used for this study:

**Mild:** Awareness of signs or symptoms, but easily tolerated and transient; causing no loss of time from normal activities; symptoms would not require medication or a medical treatment; signs and symptoms are transient.

**Moderate:** Marked symptoms and discomfort severe enough to cause moderate interference with the subject's usual activities. Symptomatic treatment is possible.

**Severe:** Incapacitating with inability to do work or usual activities; signs and symptoms may be of systemic nature or require medical intervention and/or treatment. Hospitalization may be required or prolonged.

The relationship of an AE or SAE to the underlying disease or to the procedure will be attributed using the following definitions:

Not Related: There is no evidence that the event has a relationship to the drug(s).

**Possibly Related**: The event has a timely relationship to the drug(s) used. However, a potential alternative etiology may be responsible for the adverse event.

**Probably Related**: The event has a timely relationship to the drug(s) used and the causative relationship can clearly be established. No potential alternative etiology is apparent.

The number of subjects and observation time in this pilot study is insufficient to develop a composite index or statistical plan for the evaluation of safety endpoints for this study. Therefore, all adverse events, their timing, severity, and attribution will be reported in study reports.

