## 6.4 Measures to Protect the Participant

All participants will have laboratory monitoring of CBC, T4, TSH, Cholesterol, INR, Sirolimus level and complete metabolic panel (CMP) at baseline, 28 days, and 56 days. Side effects may receive imatinib dose reduction to 200 mg daily if persistent. Study withdrawal for side effects is permitted. All side effects will be graded and followed. Side effects suggestive of an infection will prompt cessation of subsequent doses of rapamycin and imatinib mesylate/placebo for 1 week until such symptoms are improved. Any worsening of symptoms would prompt evaluation. Decline in FEV1 or FVC of 10% would prompt end of study, study unblinding, and transition to usual clinical care. A study

coordinator will call each participant to check on how they are doing 1 week +/- 3 days and 2 weeks +/- 3 days after the baseline visit and 2 weeks +/- 3 days after the 1 month study visits.

Study related injuries are addressed in the MUSC Statements of the informed consent form. In the event of a study related injury, the participant should go immediately to the emergency room of the Medical University Hospital, or in case of an emergency go to the nearest hospital, and tell the physician on call that they are in a research study. The doctor should call the study doctor to make arrangements for treatment. If the study sponsor does not pay for treatment, the Medical University Hospital and the physicians who render treatment will bill the participant's insurance. If the insurance company denies coverage or insurance is not available, the participant will be responsible for payment of all services rendered.

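### The adverse event severity scale in 6.3.1 has no laboratory criteria, and its transience condition leaves some persistent events with no grade

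*Combined protocol and SAP*

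**What the plan says.** Section 6.3 includes in its definition of an adverse event any "clinically significant abnormal laboratory value or change in value". Section 6.3.1 has the form record "Event, date of onset, severity, duration, and relationship to sirolimus or imatinb", where it can be determined, and introduces one scale with: "The following general definitions for rating severity should be used for this study".

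The three levels are:
- **Mild:** "Awareness of signs or symptoms, but easily tolerated and transient; causing no loss of time from normal activities", continued by "symptoms would not require medication or a medical treatment; signs and symptoms are transient". Transience is thus required twice.
- **Moderate:** "Marked symptoms and discomfort severe enough to cause moderate interference with the subject's usual activities", with a note that symptomatic treatment is possible.
- **Severe:** incapacity for work or usual activities comes first. The text then says that signs and symptoms may be systemic or may need medical intervention or treatment, and that hospitalization may be required or prolonged.

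Section 6.4 adds: "All side effects will be graded and followed". It schedules CBC, CMP, T4, TSH, cholesterol, INR and sirolimus level at baseline, 28 days and 56 days, and names no laboratory toxicity scale.

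Section 6.1.3 lists among the most common imatinib effects "reduced number of blood cells (any cell line can be affected"). Section 6.1.4 lists thrombocytopenia among the most common sirolimus effects.

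Section 6.3.1 disclaims any composite index or statistical plan for safety. It promises instead a report of all adverse events with their timing, severity and attribution.

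**The concern.** A severity scale should be able to place every event that the protocol defines as adverse. This one is written for symptoms, while laboratory abnormalities are also adverse events, are looked for at every visit and are named as common effects of both drugs. Under 5.4, participants who enter on sirolimus and are randomized to imatinib take both drugs during the first month.

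The severity rating carries weight here because little else is promised. Safety is the third specific aim, 4.6 describes the trial as designed primarily for safety, and sections 1 and 2.2 want its safety data to support a phase 3 design. Sections 7.2 and 7.3 specify no summary or shift table of laboratory values that would show their depth by another route. If the scale cannot separate a slight from a deep asymptomatic abnormality, the severity rating that reaches the DSMB and the study reports cannot either.

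**Working it through.** The plan gives no figure to reproduce on this point. The check applies the 6.3.1 definitions as written to the kinds of event that 6.3 admits. It treats a laboratory abnormality as a sign, which is the reading most favorable to the scale.

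| Event | Mild | Moderate | Severe | Result |
|---|---|---|---|---|
| Laboratory, no symptoms, transient, no treatment | Met | Fails: no marked symptoms | Fails: no incapacity, no intervention | Mild, at any depth |
| Laboratory, no symptoms, persistent, no treatment | Fails: not transient | Fails: no marked symptoms | Fails: no incapacity, no intervention | No level |
| Laboratory, no symptoms, intervention needed | Fails if its no-treatment condition, worded for symptoms, extends to signs | Fails: no marked symptoms | Depends on whether the intervention clause suffices without incapacity | Ambiguous |
| Symptom, tolerable, persistent | Fails: not transient | Fails: not marked | Fails: not incapacitating | No level |
| Symptom, marked, interferes with activity | Fails | Met | Depends on degree | Gradable |

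**Depth.** No level contains a laboratory threshold. Two asymptomatic cell counts of very different depth, both transient and untreated, receive the same rating.

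**The ambiguous row.** In Severe, the intervention clause comes after incapacity and is worded with *may*. One rater can take it as sufficient alone, another as a description of incapacitating events. The two sites could grade the same value differently.

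**Where the laboratory part can arise.** Inputs: 20 participants (5.2); scheduled panels at baseline, 28 and 56 days (6.4), the baseline one before study drug.
- Post-baseline panels: 20 × 2 = 40, of which 10 × 2 = 20 are in the imatinib arm (10 sets of each treatment, section 6).
- This is a ceiling on occasions, not a count of events. Only clinically significant abnormalities are adverse events, and the documents give no rate for them.

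**What one regraded participant does.** With 10 per arm, 1/10 = 10 percentage points. Exact 95% (Clopper-Pearson) limits:
- 0 of 10 severe: upper limit 1 − 0.025^(1/10) = 0.308, so 0% to about 31%.
- 1 of 10 severe: 0.3% to 44.5%.

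The intervals overlap heavily, so regrading one participant would not change a formal inference. It would change the observed severe rate from 0% to 10%, and a descriptive listing is all that the plan offers.

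**The case against.** The strongest reply is that the scale is broader than symptoms, that its definitions are called general and so leave room for judgement, and that nothing important is lost. A reader might draw four stronger conclusions that the documents do not support.

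- *Severity rests only on symptoms and lost activity.* Mild and Severe also refer to signs and to need for treatment, and Severe to hospitalization. A deep cytopenia that needs treatment can be read as Severe. This narrows the clear gap to events needing no intervention and leaves ambiguity for the rest.
- *The severity rating is wrong for the toxicity most expected, or for liver tests.* Section 6.1.3 lists reduced blood cells last, without frequencies, after effects that are mostly symptoms and suit the scale. Neither 6.1.3 nor 6.1.4 lists a liver test rise, and the CMP components are not given.
- *Every laboratory test, or every laboratory adverse event, is affected.* Tests performed are not adverse events, and symptomatic events can be graded.
- *The DSMB would miss serious toxicity.* The board reviews all adverse events quarterly. Death, life-threatening events, hospitalization and intervention to prevent permanent impairment follow the SAE route in 6.3.2 and 6.3.3 whatever the severity rating.

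It is also true that the imatinib dose reduction in 6.1.3 and 6.4 is permitted for persistent side effects without reference to a severity level, so the gap alters no stated action.

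What stands after this is the rating itself. Seriousness is a different attribute from severity and does not fill that field. Leaving the missing cases to judgement invites differences between two sites.

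**Conclusion.** The point holds as a defect of the severity rating and no further. As written, an asymptomatic laboratory event needing no treatment is Mild at any depth if transient and has no level if it persists. One needing intervention is graded ambiguously, and a tolerable but persistent symptom has no level. Detection, listing and serious-event reporting are intact.

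The number of misgraded events is unknown. The conclusion rests on applying 6.3.1 literally and on no laboratory grading scale standing elsewhere in the documents. It should be corrected because severity is one of the few safety outputs promised in a trial with safety as an aim, and the correction is cheap. It does not call the trial's safety oversight into question.

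**What to change.** In 6.3.1 and on the adverse event form:

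1. Grade laboratory adverse events by value, using a named published scale and version (for example CTCAE).
2. State how its grades map to the single severity field, for example grade 1 = Mild, grade 2 = Moderate, grade 3 or higher = Severe. Without this the form would hold two scales that cannot be tabulated together.
3. Keep the three existing definitions for symptoms.
4. Delete both transience conditions from Mild. Duration is already a separate field, so no information is lost.

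The cost is a change of wording and a minor change to the form, with no added visit, sample or participant. The small downside is that some laboratory events will carry a higher grade than they would now.

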## **3. STUDY OBJECTIVES**

## 3.1 Primary Aim

## To determine whether imatinib mesylate will be equivalent to sirolimus in short term efficacy and safety in patients with LAM.

The primary efficacy analysis will be the log transformed change in intrasubject plasma VEGF-D before and 1 month after initiation of monotherapy imatinib mesylate.

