## 3.2 Secondary Aims

1) To determine if monotherapy imatinib mesylate suppresses serum VEGF-D in LAM compared to placebo.

2) To determine if sirolimus (rapamycin) withdrawal for 1 month is associated with serum VEGF-D elevation in patients on imatinib mesylate.

3) To determine the safety of imatinib mesylate in patients with LAM.

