## 4.4 Laboratory Analysis

Samples of whole blood serum, DNA, blood mononuclear RNA, and urine will be obtained during this study. These samples serve the dual purpose of allowing a robust safety analysis of study timepoints and populating a LAM biobank of biosamples that are available to the larger LAM community (see Data Resource Sharing attachment). Biosamples will be stored both at Columbia University and MUSC and shared between laboratories with a sample and data sharing agreement in place with this study.

VEGF-D level will be measured at the beginning of the study, at one month and at the end of the study (56 days). For safety, all participants will also have laboratory monitoring of CBC, T4, TSH, Cholesterol, Sirolimus level and complete metabolic panel (CMP) at baseline, 28 days, and 56 days.

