## 4.6 Questionnaires

LAM is marked by premature disability, a shortened lifespan in most individuals, and frequent symptoms of disease. Disease specific quality of life, general quality of life, measures of exacerbation frequency, pre-existing lung function decline, and measures of dyspnea are collected by standardized and validated instruments. Quality of life questionnaire instruments are described in a later attachment as guided by the CDMRP program. Improved quality of life was determined among MILES study participants treated with sirolimus. Similarly, such measures will be collected in this imatinib pilot study.

Designed primarily as a safety study, the likelihood of achieving statistical differences between the groups in lung function or quality of life remains low; therefore, the questionnaires used in the study should be viewed as secondary and exploratory endpoints as explained in Attachment 1. We will not be modifying any instrument for this study and will use the most recent validated version for each tool utilized. Recently, the St. Georges Respiratory Questionnaire (SGRQ) has been demonstrated to have longitudinal construct validity in LAM Specifically, the SGRQ is a self-administered respiratory specific health care quality of life tool. When compared to FEV1, diffusion of the lung for carbon monoxide (DLCO), 6 minute walk test distance, and VEGF-D levels from the MILES cohort, the SGRQ change scores tracked for each of these four anchors. The strongest correlates were with FEV1. Plots of cumulative distribution functions further supported the longitudinal validity of the SGRQ in LAM.

The SGRQ is a 50 question examination that is available for use to academic investigators without charge. It is scored 1-100 with a clinically meaningful difference in obstructive lung diseases of 4 points change. Test to test reproducibility ranges from 0.795 to 0.9 for the American version that will be used for this study as a secondary variable. A copy of the questionnaire follows.

Exploratory endpoints for the study include mMRC dyspnea scale, the functional Assessment Inventory, and the EQ-5D score that were all used in the MILES study in a LAM population. None have been independently validated in LAM, yet in this pilot study, will be used to define if a treatment signal exists with these questionnaires. All have been used in more common respiratory diseases.

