## 5. STUDY DESIGN AND PROCEDURES

## 5.1 Overview

The proposed study design is a prospective, multicenter, randomized, stratified, double blind, placebocontrolled, proof of principal trial to examine the effect of imatinib mesylate on intrasubject VEGF-D, a biomarker associated with LAM disease activity.

The study is designed as a 3 visit study including baseline, 1 month, and 2 month visits. Since most patients with impaired lung function who would be eligible for this study are already on sirolimus, the proposed study would simultaneously address three issues: 1) provide a biomarker rich proof of principle study of imatinib mesylate in LAM, 2) determine if imatinib mesylate is safe when added to sirolimus, and 3) determine if imatinib mesylate controls vascular endothelial growth factor-D (VEGF-D) once sirolimus is removed. Small numbers of individuals are not on sirolimus; however, this proposal would not exclude them to define if there is a treatment response signal to imatinib mesylate alone. A stratified randomization strategy will differentially enroll participants on or off rapamycin at baseline.

At the conclusion of the study, participants will be returned to clinically available LAM therapy chosen with their treating physician. Imatinib will not be available through the investigators after participation in this study.

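### Section 6.3.1 declines a statistical plan for safety, in conflict with the plan's safety aims; small numbers argue against testing event counts, not against by-arm safety estimates

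*Combined protocol and SAP*

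**What the plan says.** Safety appears in the plan's purposes at several levels.

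- Section 3.1 (primary aim): "To determine whether imatinib mesylate will be equivalent to sirolimus in short term efficacy and safety in patients with LAM". The primary hypothesis in section 2.3 makes the same claim.
- Section 3.2, third secondary aim: "To determine the safety of imatinib mesylate in patients with LAM".
- Section 5.1 lists, among the questions the trial addresses, to "determine if imatinib mesylate is safe when added to sirolimus".
- Section 4.6: "Designed primarily as a safety study".
- Section 4.4 says the samples serve the purpose of "allowing a robust safety analysis of study timepoints".

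Section 6.4 gives all participants, hence both arms, "laboratory monitoring of CBC, T4, TSH, Cholesterol, INR, Sirolimus level and complete metabolic panel (CMP) at baseline, 28 days, and 56 days".

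The last paragraph of section 6.3.1 then states that participants and observation time are "insufficient to develop a composite index or statistical plan for the evaluation of safety endpoints for this study", and that therefore "all adverse events, their timing, severity, and attribution will be reported in study reports". Sections 7.2 and 7.3 define primary, secondary and exploratory analyses of VEGF-D, lung function, walking distance, dyspnea and quality of life. None of them uses an adverse event or a safety laboratory value.

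**The concern.** The placebo arm is what allows imatinib effects to be separated from LAM, from sirolimus and from chance. A report of events with investigator attribution does not use it. Attribution is least dependable in the first month, when participants who entered on sirolimus take it with imatinib or with placebo, and section 6.1.3 describes a known interaction that raises sirolimus levels. The question in section 5.1 about adding imatinib to sirolimus belongs to that month; sirolimus is stopped at the 1 month visit, so events in the second month answer a different question.

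The laboratory values have no planned use beyond individual monitoring, unless a value is recorded as a clinically significant abnormality and so becomes an adverse event under section 6.3. A moderate shift across the imatinib arm, with no single value flagged, would appear in no planned output.

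At stake is what the trial may conclude about safety. The Introduction says its safety data should be sufficient to design a phase 3 study. With no by-arm estimates and no intervals, a clean result in about ten exposed people could be reported as safety determined, or as equivalence to sirolimus in safety, when the data could show neither.

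**Working it through.** The documents give no safety event rate, margin, standard deviation or power, so there is no stated figure to reproduce. The check asks two things: does the small-numbers reason hold, and what does it rule out?

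**Inputs.** N = 20 (section 5.2). Ten per arm, inferred from the 10 imatinib and 10 placebo sets packaged (section 6). Two-sided 0.05 (section 7.2). Event rates and SD units below are assumptions.

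**1. Tests of event counts, 10 v 10, Fisher's exact test.** Significance needs at least 5 v 0 (p = 0.033), 7 v 1 (p = 0.020) or 8 v 2 (p = 0.023). Power is the sum of the two binomial probabilities over all significant tables:

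| Assumed rates, imatinib v placebo | Power |
|---|---|
| 30% v 10% | 6% |
| 40% v 10% | 15% |
| 50% v 10% | 30% |
| 60% v 10% | 47% |
| 80% v 10% | 84% |

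Detecting 30% v 10% with 80% power would take about 62 per arm (normal approximation). For tests, the reason in section 6.3.1 is sound.

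**2. Estimates of event rates.** With no events in n participants, the exact two-sided 95% upper limit is 1 − 0.025^(1/n).

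- n = 10: 1 − 0.025^(0.1) = 0.308, or 31%. One-sided: 1 − 0.05^(0.1) = 0.259, or 26%.
- For imatinib added to sirolimus, n is the number in the imatinib arm on sirolimus at baseline. The plan says only that the majority of participants will be. For an assumed n of 6 to 10, the limit runs from 1 − 0.025^(1/6) = 46% down to 31%.
- 3/10 has an exact 95% CI of 7% to 65%. 3/10 v 1/10 is a difference of +20 points, with a Newcombe 95% CI of −16 to +51.

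These intervals are wide but computable, and they state how little is known. Ten participants are still informative about common events: the chance of seeing at least one is 1 − (1 − p)^10, which is 89% at p = 20%, 65% at 10% and 40% at 5%.

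**3. Laboratory changes.** For a difference in mean change between arms, the 95% CI half-width is t(0.975, 18 df) × √(2/10) × SD = 2.101 × 0.447 × SD = 0.94 SD. A single t-test has 56% power at 1 SD and 80% at 1.32 SD; the rank-sum test has about 53% and 75%. Only large shifts would stand out, but an estimate is available for every analyte.

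**4. The plan's own practice.** The table in section 7.3.3 has 8 × 3 = 24 cells: 1 primary, 4 secondary and 24 − 1 − 4 = 19 exploratory. Section 7.2 analyses exploratory endpoints without multiplicity adjustment. One column is the change from baseline to 1 month in patients on sirolimus, which is the combination period. The plan thus treats 20 people as enough for exploratory efficacy comparisons, including the split that section 5.1 needs for safety.

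**5. The equivalence wording.** No safety margin is given. Nor does the design contain a randomised comparison of imatinib alone with sirolimus alone: participants who entered on sirolimus take it in both arms in month 1 and in neither arm in month 2, and sirolimus-naive participants do not take it.

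**The case against.** The best defence is that section 6.3.1 records an open, reasoned decision for a 20-person pilot, and that the power figures bear it out. For tests of event counts that stands. Other parts also stand. Reporting all events does not exclude showing them by arm. Onset dates are recorded, so events can be assigned to either month. Section 6.3 counts clinically significant laboratory abnormalities as adverse events, so extreme values are captured. Section 5.5.1 presents the laboratories as a means of finding adverse events and protecting participants. Sirolimus levels are monitored, and the DSMB reviews all adverse events quarterly. These are oversight of individuals and of conduct, however; none commits the trial to an end-of-study summary by arm.

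Three stronger readings are tempting but not supported.

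- A reader might infer that the plan promises a test of Aim 3 against placebo and fails to deliver it. Aim 1 names placebo; Aim 3 does not. The expectation of a by-arm comparison comes from the randomised placebo-controlled design, and it calls for estimates rather than a test.
- A reader might infer that laboratory changes hold most of the safety information. The common side effects listed in section 6.1.3 are mainly clinical.
- A reader might take nine of the ten imatinib participants to be on sirolimus. The 90% in section 6 is an estimate for patients with LAM and low lung function, not an enrolment figure; sections 2.2 and 7.1 say only the majority.

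Testing every analyte would also be a poor remedy. Assuming 10 to 20 analytes at two visits (20 to 40 tests) and an attained level of about 0.043 for the exact rank-sum test, 20 × 0.043 = 0.9 to 40 × 0.043 = 1.7 false positives would be expected with no drug effect. Intervals within a very small sirolimus-naive group would say almost nothing.

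**Conclusion.** The concern holds as an internal conflict with a real but limited consequence. Section 6.3.1 cannot be reconciled with the safety analysis promised in section 4.4, the description in section 4.6, the question in section 5.1 or the equivalence wording in sections 2.3 and 3.1. The small-numbers reason supports not relying on tests of event counts (about 30% power at an assumed 50% v 10%). It does not support omitting by-arm event proportions with exact intervals, or leaving the laboratory values unanalysed unless flagged as adverse events.

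The size of the issue is the gap between the claim and the data: a rate of up to 31% is compatible with no events in 10. That figure assumes ten imatinib participants, all treated and followed; with fewer the limit is higher. The change should be made before unblinding, because it determines what the trial may say about safety. It does not affect the VEGF-D analysis.

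**What to change.** Replace the last paragraph of section 6.3.1 and add a safety paragraph to section 7.2, along these lines:

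> Safety will be described, not tested for equivalence. Numbers and proportions of participants with any adverse event, each adverse event, a serious adverse event, and discontinuation of study drug will be given by randomised arm, regardless of attribution, with exact 95% confidence intervals, separately for Days 0–28 and Days 28–56. Results for Days 0–28 will also be shown for participants on sirolimus at baseline. Sirolimus-naive participants will be shown as counts only if few. When no event is seen, the exact upper limit will be reported. Change from baseline to Day 28 and Day 56 in each safety laboratory value will be given by arm, with the between-arm difference and 95% interval, as exploratory; any p-values are secondary because many analytes are examined.

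Three wording changes go with it.

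- Restate Aim 3 (Specific Aims and section 3.2) as describing safety.
- Remove the claim of equivalence in safety from sections 1, 2.3, 3.1 and 4.2, or restate it as descriptive. Changing Aim 3 alone would leave it standing.
- Bring sections 4.4 and 4.6 into line with the new paragraph, and settle the laboratory list: INR is in sections 5.5.1, 6.1.3 and 6.4 but absent from section 4.4 and Table 2.

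The cost is a protocol and SAP wording change, a few extra tables, and a more modest safety claim. No extra participant, visit or sample is needed.
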